1 INTRODUCTION

Major changes to the protocol-planned analyses are described in [Section 3.9](#).

1.1 STUDY DESIGN

This is a Phase 2, multi-cohort, un-controlled, non-randomized, open-label, multi-center study assessing the antitumor activity and safety of SAR444245 combined with other anticancer therapies in participants with HNSCC.

The study consists of a core phase for all cohorts, with a safety run-in and an expansion phase for specific cohorts. The results of an interim analysis after the core phase will decide if the expansion phase will be opened. An overview of the study intervention and disease being treated for each cohort is provided in the table below.

Cohort	Study intervention	Disease
A1	SAR444245 + pembrolizumab	R/M HNSCC treatment-naïve for R/M disease, PD-L1 CPS ≥ 1
A2	SAR444245 + cetuximab + pembrolizumab	R/M HNSCC treatment-naïve for R/M disease, PD-L1 CPS ≥ 1
B1	SAR444245 + pembrolizumab	R/M HNSCC treated with PD1/PD-L1-based regimen & platinum based regimen after failure of no more than 2 regimens for R/M disease
B2	SAR444245 + cetuximab	R/M HNSCC treated with platinum-based regimen & cetuximab-naïve after failure of no more than 2 regimens for R/M disease

CPS: combined positive score; HNSCC: Head and neck squamous cell carcinoma ; PD1: Programmed cell death protein 1; PD-L1: programmed cell death-ligand 1; R/M: Recurrent/metastatic.

Participants who are eligible for both Cohorts A1 (to receive SAR444245 and pembrolizumab) and A2 (to receive SAR444245, pembrolizumab and cetuximab) should be enrolled in Cohort A1 until Cohort A1 enrollment is completed, meaning that cohort A2 will start after cohort A1 completion. For each cohort, SAR444245 will be administered at 24 $\mu\text{g}/\text{kg}$ Q3W. The level might be reduced to [] $\mu\text{g}/\text{kg}$ [] or another lower dose level. Cetuximab will be administered at a dose of 400 mg/m² as an IV infusion on Cycle 1 Day 1 of the study followed by subsequent doses of 250 mg/m² cetuximab IV QW (cohorts A2 and B2). The planned dose of pembrolizumab for this study is 200 mg Q3W (cohorts A1, A2 and B1).

1.2.1 Estimands

Primary estimand defined for main efficacy endpoints are summarized in below [Table 2](#). More details are provided in [Section 3](#).

Table 2 - Summary of primary estimand for main endpoints

Endpoint Category (estimand)	Estimands			
	Endpoint	Population	Intercurrent event(s) (IE) handling strategy	Population-level summary (Analysis and missing data handling)
Primary objective: To determine the antitumor activity of SAR444245 in combination with other anti-cancer therapies				
Primary endpoint (estimand 1)	Objective Response (OR) (confirmed CR or PR)	Efficacy	
 While not initiating new anti-cancer therapy (NAT) - Regardless of early IMP discontinuation (treatment policy strategy) 	ORR, defined as the percentage of the participants with objective response (CR or PR) as best overall response. The confidence interval (CI) will be calculated using Clopper Pearson methods.
Secondary objective: To assess other indicators of antitumor activity of SAR444245 in combination with other anti-cancer therapies				
Secondary endpoint (estimand 2)	DOR	Responders from efficacy population	
 Had NAT not been initiated (hypothetical strategy) Regardless of early IMP discontinuation (treatment policy strategy) - Had two or more consecutive tumor assessments not been missed/unevaluable immediately before documented progression or death (hypothetical strategy) 	The Kaplan Meier estimate and corresponding CI of DOR at specified time points. The quantiles of DOR and corresponding CI will be calculated from Kaplan Meier method.
Secondary endpoint (estimand 3)	PFS	Efficacy	
 Had NAT not been initiated (hypothetical strategy) Regardless of early IMP discontinuation (treatment policy strategy) - Had two or more consecutive tumor assessments not been missed/unevaluable immediately before documented progression or death (hypothetical strategy) 	The Kaplan Meier estimate and corresponding CI of PFS at specified time points. The quantiles of PFS and corresponding CI will be calculated from Kaplan Meier method.

2 ANALYSIS POPULATIONS

The following populations for analyses are defined. Unless otherwise specified, these populations will be applicable for both safety run-in and dose expansion parts. The participants included in the safety run-in part, if fulfilling the inclusion criteria of the expansion part and if the planned dose and dosing schedule are the same as in dose expansion will be included in the analyses of dose expansion.

Table 3 - Populations for analyses

Population	Description
Screened	All participants who have given their informed consent.
Enrolled	All participants who have given their informed consent and have been allocated to an intervention (by IRT) regardless of whether the intervention was received or not.
Exposed	All participants who have given their informed consent and received at least one dose (even incomplete) of IMP (SAR444245 or cetuximab or pembrolizumab).
Population without trial impact (disruption) due to COVID-19	All exposed participants: 
without any critical or major deviation related to Coronavirus disease 2019 (COVID19)and who did not permanently discontinue treatment due to COVID-19and who did not permanently discontinue study due to COVID-19
Efficacy	All participants from the exposed population with at least one evaluable post-baseline tumor assessment or who permanently discontinued study treatment.
DLT-evaluable	All exposed participants in the run-in period who have been treated and observed for at least 21 days. Any participants who have experienced a DLT during DLT observation period will also be DLT-evaluable.
Response-evaluable	All participants from efficacy population with an evaluable baseline and at least one evaluable post-baseline tumor assessments. Participants who died from disease progression before any TA will also be response evaluable.
Pharmacokinetic (PK)	All participants from exposed population with at least 1 PK concentration available after the first dose of study intervention.
ADA	All participants from exposed population with at least 1 ADA result (positive, negative, or inconclusive) after the first dose of study intervention.
Pharmacodynamics (PDy)	All participants from the exposed population with at least 1 PDy parameter assessed after the first dose of study intervention.

Participants exposed to study intervention before or without being enrolled will not be considered enrolled and will not be included in any analysis population. The safety experience of these participants will be reported separately.

For any participant enrolled and treated more than once, only the data associated with the first enrollment will be used in any analysis population. The safety experience associated with any later enrollment will be reported separately.

3 STATISTICAL ANALYSES

3.1 GENERAL CONSIDERATIONS

In general, continuous data will be summarized using the number of observations available, mean, standard deviation (SD), median, minimum, and maximum. Categorical and ordinal data will be summarized using the count and percentage of participants.

The baseline value is defined as the last available value before the first administration of any of the three IMPs (SAR444245 or cetuximab or pembrolizumab). For participants enrolled but not treated, the baseline value is defined as the last available value before enrollment.

Unless otherwise specified, analyses will be performed by cohort, by dose and overall (if applicable). Participants enrolled in the safety run-in part and treated at the RP2D will be included in the analyses of the core phase.

All efficacy analyses will be performed on the efficacy population. Objective Response Rate (ORR), as well as all other response-related efficacy endpoints will be primarily derived using the Investigator's assessment for all cohorts and using Response Evaluation Criteria in Solid Tumor (RECIST 1.1).

Central imaging may be done retrospectively if significant activity is observed (See [Section 3.2.3](#) for sensitivity analysis).

Confidence intervals will be two-sided 90% CI for efficacy analyses and will be used for descriptive purposes only, without inference.

The BOR is defined as the best overall response observed from the date of first investigational medicinal product (IMP) until disease progression, death, cut-off date or initiation of further anti-cancer therapy, whichever occurs first. Also:

- A PR or a CR must be confirmed on a second imaging done at least 4 weeks apart, in order to confirm the antitumoral response.
- A SD response must be assessed at least 6 weeks after the first IMP administration to be considered as evaluable.

All safety analyses will be performed on the exposed population.

Analysis period

The analysis period will be divided into 3 segments:

- The **pre-treatment period** is defined as the time from when the participants give informed consent to the first administration of the IMP.
- The **on-treatment period** (ie, treatment-emergent [TE] period) is defined as the time from the first administration of IMP up to 30 days after the last administration of IMP.

- The **post-treatment period** is defined as the time from the end of the on-treatment period, ie, 31 days after the last administration of IMP.

3.2 PRIMARY ENDPOINT(S) ANALYSIS

3.2.1 Definition of endpoint(s)

The primary endpoint is the ORR.

The ORR is defined as the proportion of participants who have a BOR (see [Section 3.1](#)) as confirmed CR or PR.

3.2.2 Main analytical approach

The primary endpoint, ORR, will be analyzed with the estimand 1, introduced in [Section 1.2.1](#), and defined according to the following attributes:

- The endpoint is confirmed objective response (confirmed CR or PR)
- The treatment condition is SAR444245 in combination with other anti-cancer therapies.
- The analysis population is the efficacy population
- Intercurrent events (IE):
 - The new anticancer therapy IE will be handled with the “**while not initiating new anti-cancer therapy**” strategy; confirmed objective response will be assessed based on tumor assessments up to the time of new anticancer therapy.
 - The early IMP discontinuation IE will be handled with the “**treatment policy**” strategy; confirmed objective response will be assessed based on tumor assessments irrespective of IMP discontinuation.
- Population-level summary will include the ORR and CI using the Clopper-Pearson method. In absence of confirmed OR, participants will be considered as non-responders, whatever the reason (including participants with missing or non-evaluable BOR).

3.2.3 Sensitivity analysis

Central imaging reading may be done retrospectively if significant activity is observed. Objective response rate (ORR) may be presented based on central imaging assessment, using the same estimand as for the primary analysis.

3.2.4 Supplementary analyses

ORR will be presented for the response-evaluable population.

This supplementary analysis will be provided using an estimand defined according to the following attributes:

- The endpoint is ORR.
- The treatment condition is SAR444245 in combination with other anti-cancer therapies.
- The analysis population is the response-evaluable population.
- Intercurrent events and their handling strategy will be the same as for ORR estimand defined in [Section 3.2.2](#).
- Population-level summary will be the same as for ORR estimand defined in [Section 3.2.2](#).

The BOR will also be summarized with descriptive statistics.

3.3 SECONDARY ENDPOINT(S) ANALYSIS

The secondary endpoints detailed in this section are the efficacy endpoints. Other secondary endpoints analyses are defined in [Section 3.6](#) (safety), [Section 3.7.1.1](#) (PK) and [Section 3.7.1.2](#) (immunogenicity).

3.3.1 Efficacy secondary endpoint(s)

3.3.1.1 *Definition of endpoint(s)*

The time to response (TTR) is defined as the time from the first administration of IMP to the first tumor assessment at which the overall response was recorded as PR or CR that is subsequently confirmed.

The duration of response (DOR) will be defined as the time from the first tumor assessment at which the overall response was recorded as CR or PR that is subsequently confirmed until documented PD before the initiation of any subsequent anti-cancer therapy or death due to any cause, whichever occurs first.

The clinical benefit rate (CBR) is defined as the proportion of participants with clinical benefit: confirmed CR or PR as BOR, or SD lasting at least 6 months (overall response recorded as SD at 6 months, ie, 26 weeks or later from first IMP intake, allowing for the ± 7 days visit window for tumor assessment scheduled at 27 weeks).

The progression-free survival (PFS) is defined as the time from the date of first IMP administration to the date of the first documentation of objective PD, or death due to any cause, whichever occurs first.

3.3.1.2 Main analytical approach

The time to response (TTR) will be assessed on the subgroup of participants who have achieved confirmed OR and will be summarized using descriptive statistics.

The analyses of DOR and PFS are based on estimands 2 and 3 introduced in [Section 1.2.1](#), and defined according to the following attributes:

- The endpoints are DOR and PFS.
- The treatment condition is SAR444245 in combination with other anti-cancer therapies.
- The analysis population for DOR corresponds to all participants from the efficacy population who achieve either confirmed PR or confirmed CR.
- The analysis population for PFS corresponds to all participants from the efficacy population.
- Intercurrent events:
 - The new anticancer therapy IE will be handled with the **hypothetical** strategy: DOR and PFS will be assessed based on tumor assessments had a new anticancer therapy not being taken. DOR and PFS will be assessed based on tumor assessments up to the time of new anticancer therapy.
 - The early IMP discontinuation IE will be handled with the **treatment policy** strategy: DOR and PFS will be assessed based on tumor assessments irrespective of IMP discontinuation.
 - Two or more consecutive missing/unevaluable tumor assessments immediately before documented progression or death will be handled with the **hypothetical** strategy: DOR and PFS will be assessed based on tumor assessments had two consecutive tumor assessments not been missed immediately before documented progression or death.
- Population-level summary will include the Kaplan Meier estimate of DOR and PFS and corresponding CIs at specified time points. Confidence intervals for KM estimates will be estimated for each treatment group using the Kaplan Meier method and log-log approach based on a normal approximation following the Greenwood's formula. The quantiles of DOR and PFS and corresponding CI from Kaplan Meier method will also be provided, CI will be constructed using a log-log transformation of the survival function and the methods of Brookmeyer and Crowley. In the absence of disease progression or death before the cut-off date, DOR and PFS will be censored as indicated in [Table 4](#). Quantiles will also be provided.

Table 4 - Censoring rules for DOR and PFS

Situation	Date of progression or censoring	Outcome	Category
No baseline tumor assessments ^a	Date of first treatment intake	Censored	No baseline tumor assessments
No evaluable ^b post-baseline tumor assessments ^a	Date of first treatment intake	Censored	No evaluable post-baseline tumor assessments
Progression documented at or between scheduled visits	Date of the first tumor assessment documenting progression	Event	Documented progression
New anticancer treatment before documented progression	Date of the last evaluable tumor assessment before new treatment	Censored	New anticancer treatment
Death prior to the first planned post-baseline tumor assessment ^a	Date of death	Event	Death
Death at or between scheduled visits	Date of death	Event	Death
Death or documented progression immediately after two ^c or more missed or non-evaluable tumor assessments	Date of the last evaluable tumor assessment documenting no progression	Censored	Death or progression after two or more missed/unevaluable tumor assessments
Alive and no documented progression	Date of the last evaluable tumor assessment	Censored	Alive without documented progression

a Not applicable for DOR.

b Evaluable TA means an evaluation different from non-evaluable.

c Two consecutive tumor assessments are considered as missed/non-evaluable if the duration between two consecutive tumor assessments done (non-missing) and evaluable is strictly longer than 20 weeks.

The clinical benefit rate will be summarized using the same estimand as for the primary endpoint.

3.3.2 Supportive secondary endpoint(s)

Not applicable.

3.4 TERTIARY/EXPLORATORY ENDPOINT(S) ANALYSIS

3.4.1 Definition of endpoint(s)

[REDACTED]

[REDACTED]

[REDACTED]

[REDACTED]

3.4.2 Main analytical approach

[REDACTED]

[REDACTED]

[REDACTED]

3.5 MULTIPLICITY ISSUES

No formal testing will be performed. Therefore, no multiplicity issues need to be addressed.

3.6 SAFETY ANALYSES

The analysis of the safety variables will be descriptive, and no testing is planned.

3.6.1 Extent of exposure

If applicable, summaries will be provided by trial impact (disruption) due to COVID-19.

3.6.1.1 *Overall exposure*

The dose information will be assessed by the following variables:

- Overall number of cycles started, defined by the number of cycles in which at least one dose of any study interventions is administered.
- Duration of IMP exposure (in months) is defined as: (Last day of exposure – first day of exposure +1)/30.4375.
- The first day of exposure is defined as the first administration date with non-zero dose for at least one of the IMP (SAR444245 or cetuximab or pembrolizumab).

The last day of exposure is the day before the theoretical date of the next administration (after the last administration), defined as the maximum between:

- The last administration date + 20 days for SAR444245,
- The last administration date + 6 days for cetuximab.
- The last administration date + 20 days for pembrolizumab.

The total number of cycles started, and cumulative total number of cycles started by participants will be summarized by category. The duration of overall exposure will be summarized quantitatively.

The following variable will be computed to describe overall dose modification (cycle delay):

- Cycle delay: A cycle is deemed as delayed if the start date of the current cycle – theoretical duration of a cycle – start date of the previous cycle is ≥ 4 days. Cycle delay is not defined for the first cycle.

Cycle delay will be analyzed at the participant (with number of participants used as denominator) and cycle (with number of cycles used as denominator) levels, as follows:

- Number (%) of participants with at least 1 cycle delayed
 - Number (%) of participants with a cycle delayed between 4 and 7 days (using maximum delay across all cycles)
 - Number (%) of participants with a cycle delayed more than 7 days (using maximum delay across all cycles)
- Number (%) of cycles delayed
 - Number (%) of cycles delayed between 4 and 7 days
 - Number (%) of cycles delayed more than 7 days.

3.6.1.2 SAR444245 exposure

The dose information will be assessed by the following:

- Duration of SAR444245 exposure (in months) is defined by (date of last administration of SAR444245 + 21 – date of first administration of SAR444245)/30.4375.
- Total number of cycles started for SAR444245 per participant
- Actual dose ($\mu\text{g}/\text{kg}$)
- Cumulative dose ($\mu\text{g}/\text{kg}$): the cumulative dose is the sum of all actual doses of SAR444245, given from first to last administration
- Actual dose intensity (ADI in $\mu\text{g}/\text{kg}/\text{week}$): defined as the cumulative dose divided by the duration of SAR444245 exposure (in weeks)
- Planned dose intensity (PDI in $\mu\text{g}/\text{kg}/\text{week}$): corresponds to the planned dose at C1D1 and divided by the theoretical cycle duration expressed in weeks (ie, 3 weeks)
- Relative dose intensity (RDI, in %): $100 \times \frac{\text{ADI } (\mu\text{g}/\text{kg}/\text{week})}{\text{PDI } (\mu\text{g}/\text{kg}/\text{week})}$

The total number of cycles started; number of cycles started by participant will be summarized by category. Duration of SAR444245 exposure, cumulative dose, ADI and RDI will be summarized quantitatively and RDI will also be summarized by category if relevant.

The following variables will be derived to describe dose modifications and dose interruptions:

- Dose reduction: The first administration will not be counted as a dose reduction. For the second and subsequent SAR444245 administrations, dose reduction will be determined using the dose level intervals provided in [Table 5](#), by comparing the current dose level to the previous dose level. If the current dose level is below the dose level interval of the previous dose administration, then the current dose level is considered reduced.

Table 5 - SAR444245 dose reduction criteria

Actual dose level	Dose level interval
8 µg/kg	
16 µg/kg	
24 µg/kg	

- Dose omission is defined as a dose not administered at the scheduled visit.
- Dose interruption: A dose will be considered as interrupted if SAR444245 administration is stopped during an infusion regardless of whether it is restarted or not.

Dose modifications and dose interruptions will be analyzed by participant and dose as follows:

- **Participant** (number of participants treated will be used as denominator)
 - Number (%) of participants with at least 1 dose modification
 - Number (%) of participants with at least 1 dose reduction
 - Number (%) of participants with at least 1 dose omission
 - Number (%) of participants with at least 1 dose interruption
 - Number (%) of participants with at least 1 dose interrupted and restarted
 - Number (%) of participants with at least 1 dose interrupted and not restarted
 - Number (%) of participants with at least 2 dose interruptions
- **Dose** (number of doses started will be used as denominator)
 - Number (%) of doses
 - Number (%) of dose interruptions
 - Number (%) of doses interrupted and re-started
 - Number (%) of doses interrupted and not re-started
 - Number (%) of doses interrupted more than once,
 - Number (%) of doses interrupted at 1st dose, 2nd dose, subsequent doses,
 - Time from dose start to first interruption in minutes summarized as a continuous variable and by category.

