c Death within 30 days from last IMP administration and for whom cause of death is not disease progression or the death occurred more than 30 days from last IMP administration and the cause of death is AE

Analysis of deaths

In addition to the analyses of deaths included in [Table 6](#), the number (%) of participants in the following categories will be provided:

- Deaths during the treatment-emergent and post-treatment periods by main reason for death
- An overview of Grade 5 AEs will be provided with the following categories:
 - Grade 5 AE (TEAE and post-treatment).
 - Fatal TEAE (regardless of date of death/period).
 - Grade 5 TEAE with a fatal outcome during the treatment-emergent period,
 - Any Grade TEAE with a fatal outcome during the post-treatment period.
 - Post-treatment Grade 5 AE (excluding a TEAE that worsened to Grade 5 during the post-treatment period).

Analysis of adverse events of special interest (AESIs)

Number (%) of participants experiencing at least one adverse event of special interest will be provided, by system organ class (SOC) and preferred term (PT). The selection will be made using the electronic case report form (eCRF) specific AESI tick box. Tables will be sorted as indicated in [Table 6](#).

In addition, the following analyses will be done for infusion reactions categories (ie, infusion related reactions [IRRs], cytokine release syndrome [CRS], flu-like symptoms [FLS] and anaphylaxis):

- Description of the infusion reactions by predefined grouping and other reported PT
- Worst grade
- Action taken for each IMP
- Corrective treatment given (Yes, No)
- Number (%) of patients with only 1 episode, ≥ 2 , ≥ 3 , ≥ 4 and ≥ 5 episodes
- Onset of first episodes of infusion reactions (at the first infusion and subsequent infusions)
- Number (%) of patients with infusion reactions (any episodes) at the first and subsequent infusions
- Number (%) of patients with at least one infusion with two episodes of infusion reactions
- Total number of infusion reaction episodes
- Time to onset from infusion (by category: infusion day/1 day after infusion/2 to 3 days from infusion/More than 3 days from infusion when applicable)
- Duration of infusion reactions (in days) (by category 1 day/2 to 3 days/more than 3 days/not recovered)
- Number (%) of patients with infusion reactions symptoms (as reported by Investigator) by SOC and PT.

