4 SAMPLE SIZE DETERMINATION

Overall, in the core phase, the plan is to treat approximately 40 participants per cohort.

The following table lists estimated ORR and the corresponding 90% exact CIs by number of responders from a sample size of 40 participants exposed in each cohort in core phase.

Table 10 - Estimated objective response rate (ORR) and 90% CI for core phase

Number of responders (N=40)	Objective Response Rate in %	90% Clopper-Pearson CI
6	15.0%	(6.7% - 27.5%)
7	17.5%	(8.5% - 30.4%)
8	20.0%	(10.4% - 33.2%)
9	22.5%	(12.3% - 36.0%)
10	25.0%	(14.2% - 38.7 %)
11	27.5%	(16.3% - 41.4 %)
13	32.5%	(20.4% - 46.6%)
15	37.5%	(24.7% - 51.7%)
17	42.5%	(29.2% - 56.7%)
19	47.5%	(33.8% - 61.5 %)
24	60.0%	(45.8% - 73.1 %)

With a sample size of 40 study participants in each cohort in the core phase, the probability of observing 1 or more instances of a specific AE with a true incidence rate of 1%, 2%, or 5% is 33.1%, 55.4%, or 87.1%, respectively. This provides reasonable assurance that events occurring at $\geq 5\%$ frequency can be identified in this study.

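### Minor: on its plain reading, SAP section 3.6.1.2 divides SAR444245 interruptions at the 1st, 2nd and later doses by all doses started, so the percentages are not interruption rates at each dose position

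*SAP*

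**What the plan says.** Section 3.6.1.2 defines an interrupted dose as follows: "A dose will be considered as interrupted if SAR444245 administration is stopped during an infusion regardless of whether it is restarted or not". Interruptions are then tabulated in two blocks. In the participant block, "number of participants treated will be used as denominator"; that block has no split by dose number. In the dose block, "number of doses started will be used as denominator". Under that heading stands the row "Number (%) of doses interrupted at 1st dose, 2nd dose, subsequent doses", with no denominator specific to it.

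No other part of the SAP restricts the denominator to doses started at the given position. Section 3.6.2 plans a split by infusion, "Number (%) of patients with infusion reactions (any episodes) at the first and subsequent infusions", but it counts patients with reactions, not interrupted doses. The cetuximab and pembrolizumab sections (3.6.1.3 and 3.6.1.4) have no dose-level block, so this row is the only planned summary of interruptions by dose position.

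**The concern.** An interruption at the first dose can happen only among first doses, of which there is one per participant treated with SAR444245. If the denominator is every dose started, it includes doses at which that event could not occur. The same holds for the second dose. The percentage for later doses rises with the number of later doses given, even if the risk per dose stays constant.

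A split by dose position is most naturally read as showing whether interruptions cluster at early infusions or persist. On the block's denominator the row partly reflects treatment duration instead. Section 3.1 has analyses done by cohort, so two cohorts with the same first-infusion risk but different durations would show different first-dose percentages.

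**Working it through.** The SAP states no numerical result for this row, so there is no figure to reproduce.

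**Inputs**
- First doses: n1 = 40, from section 4 ("in the core phase, the plan is to treat approximately 40 participants per cohort").
- Second doses: n2 = 36. This is an assumption.
- Mean SAR444245 doses per participant: m. The SAP does not give it, so it is varied from 3 to 10. Total doses = 40m, and third-or-later doses = 40m − 76.
- Interruption risks: assumed. One pattern is flat (10% at every dose) and one is falling (20% / 10% / 3%).

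**Formulas**
- Rate at position k = interruptions at position k / doses started at position k.
- Block percentage at position k = interruptions at position k / all doses started = rate × n_k / (40m).
- For the first dose n_k = 40, so the block percentage = first-dose rate / m.
- The three block percentages always add up to the overall interruption percentage.

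**Results on the block denominator (1st / 2nd / subsequent)**

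| m | Total doses | Subsequent doses | Flat 10% shows | 20/10/3% shows |
|---|---|---|---|---|
| 3 | 120 | 44 | 3.3 / 3.0 / 3.7% | 6.7 / 3.0 / 1.1% |
| 4 | 160 | 84 | 2.5 / 2.25 / 5.25% | 5.0 / 2.25 / 1.6% |
| 6 | 240 | 164 | 1.7 / 1.5 / 6.8% | 3.3 / 1.5 / 2.05% |
| 10 | 400 | 324 | 1.0 / 0.9 / 8.1% | 2.0 / 0.9 / 2.4% |

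For example, at m = 6 the flat pattern gives 4/240, 3.6/240 and 16.4/240.

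**Where the order changes.** Under 20/10/3%, later doses exceed the 2nd when 0.03 × (40m − 76) > 3.6, that is 40m − 76 > 120, so m > 4.9. At means of 3 and 4 the falling order is kept. Under the flat pattern the display is nearly flat at m = 3, about doubles from 1st to subsequent at m = 4 (5.25/2.5 = 2.1), and rises about fourfold at m = 6 (16.4/4 = 4.1).

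**A second falling pattern.** With risks of 20/10/5% and the same 40 and 36 doses, the true first-to-subsequent ratio is 4. On the block denominator the ratio is (40 × 0.20) / (subsequent doses × 0.05) = 160 / subsequent doses. That is 4.0, 2.0, 1.0 and 0.5 for 40, 80, 160 and 320 subsequent doses.

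**With position-specific denominators** each pattern is recovered as assumed, whatever the value of m.

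**The case against.** The strongest reply is that the SAP does not speak of total doses. The heading may mainly fix the unit of counting, doses as against participants, and a programmer could take a row about the 1st dose to mean first doses started. The heading cannot apply literally to every row in any case: the first row would always be 100%, and time to first interruption exists only for interrupted doses. This stands as an ambiguity. It does not remove the point, because the text never gives the position-specific reading and one sentence would settle it.

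Even on the plain reading the figures are arithmetically valid. They partition the overall interruption percentage by position, and the SAP states no purpose for the row. This also stands: they mislead only if read as rates at each dose.

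The rates are largely recoverable. The row reports counts, first doses started equal the participants treated with SAR444245, and cycles started are summarised in the same section. Recovery of the later rates depends on the categories chosen for that summary.

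Finally, the consequences are limited: "The analysis of the safety variables will be descriptive, and no testing is planned", and no endpoint or stated decision uses this row. That is why the point is minor.

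**Conclusion.** The point holds as a minor one. On the plain reading of section 3.6.1.2, the row shows each position's contribution to the overall interruption percentage and not the interruption rate at that position. The scaling of the first-dose figure by 1/m needs no assumption about risk: the figure shown is one third of the first-dose rate at a mean of 3 doses, one sixth at 6 and one tenth at 10. Comparisons between cohorts of different treatment duration are affected accordingly.

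A reader might infer that the table will necessarily show a false pattern across positions. The SAP does not support that, because it gives no doses per participant. Whether the pattern is distorted depends on exposure and on the assumed risks: a falling risk of 20/10/3% keeps its order at means of 3 to 4 doses and changes it only above about 4.9, and a flat risk looks nearly flat at 3 but not at 4 or more. A reader might also infer that first-infusion safety information is lost. It is not: the counts are unaffected, and first-infusion reactions are summarised separately in section 3.6.2.

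**What to change.** Add one sentence to section 3.6.1.2: for the row by dose position, the denominators are the number of first, second, and third-or-later SAR444245 doses started, respectively, with n/N shown for each. Keep all doses started as the denominator for the overall interruption rows.

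The cost is one sentence and a changed denominator in one table, with no new data. First-dose percentages will be higher than under the plain reading whenever the mean exceeds one dose. Interruption counts and all efficacy results stay the same.
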